Progression-free survival (PFS): The time between the date of enrollment and the first documented tumor progression (as per RECIST 1.1 criteria, regardless of whether treatment is continued), or death due to any cause, whichever occurs first. When determining PFS, clinical exacerbations without definite evidence of progressive disease (as per RECIST 1.1) is not considered progressive disease. For subjects who die without any prior reports of progression, the date of death is considered the date of progression. Subjects without progressive disease or death will be censored on the date of their last evaluable tumor assessment. Subjects without tumor assessments during the study or death will be censored on their date of enrollment. Subjects who discontinue the treatment for reasons other than progressive disease (no subsequent tumor assessments) will be censored on their date of study discontinuation. For subjects who have not previously reported progressive disease but have initiated subsequent anti-tumor therapy, they will be censored on the date of their last evaluable tumor evaluation before starting the subsequent anti-tumor therapy, or they will be censored when starting the subsequent anti-tumor therapy. When subjects are not censored on the date of study discontinuation or the date of starting new anti-tumor treatment, the

scheduled sensitivity analysis will confirm PFS based only on the time of radiologically confirmed progression events. The occurrence of a new tumor will not be considered a progressive disease and is not censored.

Disease control rate (DCR): the proportion of subjects with a best overall response of complete response (CR), partial response (PR), or stable disease (SD) as per RECIST 1.1 criteria. If the subject achieves CR or PR, confirmation should be done at least 4 weeks (28 days) after the first evaluation. Best overall response refers to the best response assessed by the investigator, or the best response from the date of enrollment to the first documentation of progression as per RECIST 1.1 or to the start of a new anti-tumor treatment (whichever comes first). For subjects without documented progression or new anti-cancer treatment, BOR will be determined based on all response evaluations. For subjects who continue SHR-1210 treatment beyond progression, the best overall response should be based on the efficacy assessment at the time of first documented progression as per RECIST 1.1.

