7.1.2 Criteria for efficacy evaluation

Objective response rate (ORR) as well as PFS, DCR and DoR based on tumor response will be evaluated by imaging examinations according to RECIST 1.1 (see [Appendix 3 Response Evaluation Criteria in Solid Tumors](#)).

For the record and assessment of survival, the subjects will be followed up by effective visits such as telephone calls on survival once every month after withdrawing from the study until death, lost to follow-up, withdrawal of informed consent, or study termination by the sponsor.

Assessments of tumor response include all known or suspected lesions.

Assessments of tumor response include all known or suspected lesions. Imaging includes CT or MRI scans of the chest, abdomen, or pelvis. Brain CT or MRI is performed for subjects with known or suspected brain metastasis, while bone scan and/or bone X-ray scan is performed for subjects with known or suspected bone metastasis.

Imaging assessment at screening must be performed within 28 days prior to the first study dose, and first tumor assessment during the treatment period should be performed 6 weeks (± 7 days) after starting study treatment. Imaging evaluation should be performed once every 2 cycles (6 weeks ± 7 days) in the first 12 months (first 16 cycles) during the treatment. Then it is performed once every 3 cycles (9 weeks ± 7 days) after 12 months until PD, lost to follow-up, death, withdrawal of informed consent, start of other anti-tumor treatment or study termination by the sponsor.

If the subject achieves CR or PR, conformation should be done at least 4 weeks (28 days) after the first evaluation. In case of SD, tumor assessment should be performed at least once after at least 6 weeks (± 7 days) after enrollment, and the measurements must meet the criteria for SD at least once.

The same imaging technique should be used in subsequent tumor evaluations for the same type of lesions as at screening. Anti-tumor activity assessment shall be carried out during the screening period and treatment process through radiography according to the study procedure; tumor evaluation should also be performed when progressive disease is suspected (such as exacerbation of symptoms) and upon withdrawal (if evaluation is not performed within the past 4 weeks).

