7.2.4 Progressive disease

Progressive disease is defined as the worsening of the subject's conditions caused by the indications of the study, including radiological progressions and progressions in clinical symptoms and signs. New metastases relative to the primary tumor or progressions of the previous metastases are recognized as PD. Life-threatening events, hospitalization or prolonged hospitalization, or events resulting in permanent or severe disability/incapacity/impairment of work ability, congenital anomalies or birth defects arising from the symptoms and signs of the progressive disease are not reported as SAEs. Death caused by the symptoms and signs of PD will be reported as an SAE.

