4.3 Response Criteria

4.3.1 Evaluation of target lesions

Complete response (CR): Disappearance of all target lesions. Any pathological lymph nodules (whether target or non-target) must have reduction in short axis to $< 10\text{ mm}$.

Partial response (PR): At least a 30% decrease in the sum of diameters of target lesions, compared with baseline.

Progressive Disease (PD): At least a 20% increase in the sum of diameters of target lesions, taking as reference the smallest sum on study (this includes the baseline sum if that is the smallest on study). In addition, the sum must also demonstrate an absolute increase of at least 5 mm (the appearance of one or more new lesions is also considered PD).

Stable disease (SD): Neither sufficient shrinkage to qualify for PR nor sufficient increase to qualify for PD, taking as reference the smallest sum diameters while on study.

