4.3.5 New lesions

The appearance of new malignant lesions denotes PD; therefore, some comments on detection of new lesions are important. There are no specific criteria for the identification of radiographically detected lesions; however, the finding of a new lesion should be unequivocal. For example, it

should not be attributable to differences in scanning technique, change in imaging modality, or findings thought to represent something other than tumor (for example, some new bone lesions that may be simply healing, or re-occurrence of pre-existing lesions). This is particularly important when the patient's baseline lesions show partial or complete response. For example, necrosis of a liver lesion may be reported on a CT scan report as a new cystic lesion, which it is not.

A lesion identified on a follow-up study that is not scanned at baseline will be considered a new lesion and will indicate PD. An example of this is the patient who has visceral disease at baseline and while on study has a CT or MRI brain ordered which reveals metastases. The patient's brain metastases are considered to be evidence of PD even if he/she did not have brain imaging at baseline.

If a new lesion is equivocal, for example, because of its small size, continued treatment and follow-up evaluation are required to clarify if it represents a truly new disease. If repeated scans confirm there is definitely a new lesion, then progression should be declared using the date of the initial identification.

While FDG-PET response evaluations generally need additional study, it is sometimes reasonable to incorporate the use of FDG-PET scanning to complement CT scanning in assessment of progression (particularly possible new disease). New lesions on the basis of FDG-PET imaging can be identified according to the following process:

- Negative FDG-PET at baseline, with a positive FDG-PET at follow-up is a sign of PD based on a new lesion.
- No FDG-PET at baseline and a positive FDG-PET at follow-up:
- If the positive FDG-PET at follow-up corresponds to a new site of disease confirmed by CT, PD is confirmed.
- If the positive FDG-PET at follow-up is not confirmed as a new site of disease on CT, additional follow-up CT scans are needed to determine if there is truly progression occurring at that site (if so, the date of PD will be the date of the initial abnormal FDG-PET scan).

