### 11.5.2.3 Progression free survival (PFS)

PFS refers to the time from the start of randomization to the date of objective progressive disease or death (caused by any reason), whichever occurs first. [Table 3](#) describes progressive disease, death, or censoring.

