**Table 3. Date of progressive disease, death, or censoring**

		No	Yes
1.	Does the subject have a baseline objective tumor assessment?	Censoring The date of censoring is the date of randomization	Skip to 2
2.	Are new anti-cancer drugs used before progressive disease or death?	Skip to 3	Censoring The date of censoring is the date of the last objective tumor assessment before the use of the new anti-cancer drug
3.	Has the subject experienced progressive disease?	Skip to 5	Skip to 4
4.	Is the progressive disease of the subject recorded after an unacceptably long time interval (the response evaluation is missing by > 2 times, i.e., 98 days)?	Progressive disease The date of progression is the date of earliest recorded progressive disease	Censoring The date of censoring is the date of the last objective tumor assessment before the long-term lost to follow-up
5.	Is the subject dead?	Censoring The date of censoring is the date of the last objective tumor assessment	Skip to 6
6.	Is the death of the subject recorded after an unacceptably long time interval (the response evaluation is missing by > 2 times, i.e., 98 days)?	Progressive disease The date of progression is the date of death	Censoring The date of censoring is the date of the last objective tumor assessment before the long-term lost to follow-up

The time of PFS is based on the time of the imaging examination rather than the time of the visit. The RECIST imaging examination time (targeted lesion, non-targeted lesion, and new lesion) for a special visit may be different, and the following rules apply:

- The date of progression will be based on the earliest date leading to progression.
- The date of censoring will be based on the last date of objective tumor assessment.

Survival curves will be plotted using the Kaplan-Meier method and the 95% CI for median time will be calculated using the Brookmeyer-Crowley method.

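### The protocol's PFS definition exempts an undefined 'new tumor' from progression, which contradicts its own RECIST 1.1 event if a new lesion is meant

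*Protocol*

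**What the plan says.** Protocol 7.1.1 takes as the PFS event death or the "first documented tumor progression (as per RECIST 1.1 criteria, regardless of whether treatment is continued"). The paragraph then sets its censoring rules and ends: "The occurrence of a new tumor will not be considered a progressive disease and is not censored". The term is not defined in the protocol or the SAP.

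The surrounding text treats new lesions differently:

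- **Protocol 7.1.2:** ORR, PFS, DCR and DoR "will be evaluated by imaging examinations according to RECIST 1.1", with a pointer to Appendix 3.
- **Protocol Appendix 3, 4.3.1:** under target-lesion progression, "the appearance of one or more new lesions is also considered PD". Section 4.3.3 repeats this for non-target disease.
- **Protocol Appendix 3, 4.3.5:** "The appearance of new malignant lesions denotes PD". The time-point tables in 4.4.1 code any new lesion as PD, whatever the other lesions show.
- **SAP 11.5.2.3:** "PFS refers to the time from the start of randomization to the date of objective progressive disease or death", with no exemption for a new tumor.
- **SAP, notes under Table 3:** "The RECIST imaging examination time (targeted lesion, non-targeted lesion, and new lesion) for a special visit may be different". New-lesion scans are thus among those that date progression, and the earliest date that leads to progression is used.
- **SAP Appendix 1.1:** a new lesion gives PD in every row where one is present.

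**The concern.** An endpoint definition should give one answer for each subject. Here the last sentence can be read as withdrawing part of the event defined at the start of the paragraph. On that reading, a subject whose target lesions are stable and who develops an unequivocal new metastasis has progressed under Appendix 3. Under the closing sentence of 7.1.1, the same subject has neither progressed nor been censored.

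Tumor assessments are made by the investigator (SAP 11.5) in an open-label trial (Protocol 4.3). Investigators work from the protocol, and the SAP can only analyze the progression that they record. If some apply the sentence to new lesions, progression dates come in late or not at all, and PFS is reported as longer than RECIST 1.1 would give.

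**Working it through.** The plan has no figure to reproduce here. No sample size, power or alpha depends on PFS. The check is a comparison of texts, a direction argument, and an illustration of size.

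**1. If 'new tumor' means new lesion.** Take a subject with SD in target lesions, no non-target progression and an unequivocal new lesion at a scheduled scan.

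| Rule applied | Result at that scan |
|---|---|
| Protocol Appendix 3, 4.4.1, Table 1 | PD; PFS event |
| SAP Appendix 1.1 with Table 3 | PD; PFS event at the earliest date leading to progression |
| Protocol 7.1.1, closing sentence | Not PD, not censored; follow-up continues |

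The third row is incompatible with the other two, and with the RECIST event in its own paragraph.

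**2. If 'new tumor' means a second primary cancer.** The sentence is then a workable rule: a different cancer is not progression of the study cancer, and follow-up goes on. Two loose ends remain. Appendix 3, 4.3.5 and SAP Appendix 1.1 make no exception for a second primary. And if that cancer is treated with anti-cancer drugs before progression, the new-therapy rule in 7.1.1 and question 2 of SAP Table 3 both censor the subject, whereas the sentence says no censoring.

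**3. Direction under reading 1.** For each affected subject the event is either postponed to a later progression or death, or becomes a censored time when new therapy starts. No event is brought forward. PFS is therefore lengthened.

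**4. Size under reading 1, illustration only.** Inputs:

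- Median PFS of 6.6 months, from Protocol 1.2 (an external cohort of 25 untreated patients given another PD-1 antibody with chemotherapy). It is a scale, not a forecast for this trial.
- f, the share of first PFS events that are new-lesion-only. **Assumption**; neither document gives it. Range shown: 5% to 40%.
- k, a multiplier on the remaining hazard after the ignored lesion. **Assumption**; 1, 2 and 3 shown.

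With constant hazard λ = ln 2 / 6.6 = 0.105 per month, the recorded PFS curve is

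S(t) = e^(−λt) + [f / (k(1−f) − 1)] × [e^(−λt) − e^(−k(1−f)λt)].

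For k = 1 this reduces to e^(−(1−f)λt), so the median is 6.6/(1−f): 6.6/0.95 = 6.95, 6.6/0.80 = 8.25, 6.6/0.60 = 11.00. For k = 2 and 3, S(t) = 0.5 is solved numerically. Check for f = 20%, k = 2: the coefficient is 0.20/(1.6 − 1) = 0.333. At t = 7.75, λt = 0.814, and 1.333 × 0.443 − 0.333 × 0.272 = 0.500.

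| f | k = 1 | k = 2 | k = 3 | Added months |
|---|---|---|---|---|
| 5% | 6.95 | 6.85 | 6.79 | 0.19 to 0.35 |
| 20% | 8.25 | 7.75 | 7.47 | 0.87 to 1.65 |
| 40% | 11.00 | 9.55 | 8.81 | 2.21 to 4.40 |

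If new lesions count as PD, as in Appendix 3 and the SAP, the illustrative median stays at 6.6. Across the grid the added time runs from about 0.2 to 4.4 months. That spread shows that the size is not determined by anything in the documents.

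**The case against.** **The documents do not use 'new tumor' for RECIST progression.** They say new lesions there, and imaging is ordered when new lesions are suspected (Protocol 6.2). Reading the sentence as covering new lesions makes the paragraph cancel its own event; reading it as covering second primaries does not. This stands as a plausible account of the intent. It does not make the text clear. Where the protocol means a different cancer elsewhere, in exclusion criterion 10, it refers to other malignancies.

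**The SAP already handles it.** Protocol 8.1 leaves detailed methods to the SAP, whose PFS rules count new lesions. This stands, and it removes most of the analytical risk. It does not reach progression calls made from the protocol. Protocol 8.1 also says that SAP revisions touching endpoint definitions should lead to a protocol revision, so the mismatch should not be left in place.

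**DoR.** A reader might infer that DoR is lengthened too, because SAP 11.5.2.2 requires the end of response to agree with the PFS date. The documents do not support this. That link is to the SAP's own PFS, which lacks the sentence, and protocol DoR has a separate RECIST 1.1 definition without it.

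**Size.** A reader might also take the k = 1 factors at 20% and 40% (1/0.80 = 1.25 and 1/0.60 = 1.67) as the likely inflation of the median. They rest on assumed shares and on no rise in hazard after the ignored lesion. At f = 40%, k = 3 gives 8.81/6.6 = 1.33, and a 5% share changes little.

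**Protocol 7.2.4** says "New metastases relative to the primary tumor or progressions of the previous metastases are recognized as PD". It points the same way but sits under safety evaluation, where it governs SAE reporting. It is not the efficacy definition and carries little weight here.

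**Conclusion.** The sentence is a real defect of wording in an endpoint definition. Read as new lesion, it contradicts its own paragraph, Appendix 3 and SAP Appendix 1.1, and following it would lengthen PFS. The direction is secure; the amount cannot be estimated from the documents. If only second primaries were meant, few subjects should be affected and the effect would be small.

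The consequence is limited. PFS is secondary and summarized descriptively by cohort, with no hypothesis test. The two-stage decisions (at least 4 of 19 responders, then at least 21 of 43 in cohort 1 and 13 of 55 in cohort 2) rest on ORR, and best overall response in Protocol 7.1.1 runs to RECIST progression without this sentence. A reader might infer that the reported PFS will be biased. That does not follow: it would require investigators to apply the sentence to new lesions when recording progression, or the analysis to depart from the SAP.

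**What to change.** In Protocol 7.1.1, replace the closing sentence of the PFS definition with: *An unequivocal new lesion of the study cancer is progression per RECIST 1.1 on the date first seen.* This agrees with Appendix 3, 4.3.5, which dates a lesion confirmed later to its first identification.

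If the sentence was meant for second primary malignancies, say so in those words and keep the existing censoring rule for new anti-cancer therapy. Put the same note in SAP Tables 2 and 3; both are needed because SAP 11.5.2.2 ties the end of response to the PFS date. If that was not the intent, delete the sentence and add no note.

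The cost is one protocol sentence and, at most, one note under two SAP tables. Sample size, visits and decision rules do not change.

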7.1.2 Criteria for efficacy evaluation

Objective response rate (ORR) as well as PFS, DCR and DoR based on tumor response will be evaluated by imaging examinations according to RECIST 1.1 (see [Appendix 3 Response Evaluation Criteria in Solid Tumors](#)).

For the record and assessment of survival, the subjects will be followed up by effective visits such as telephone calls on survival once every month after withdrawing from the study until death, lost to follow-up, withdrawal of informed consent, or study termination by the sponsor.

Assessments of tumor response include all known or suspected lesions.

Assessments of tumor response include all known or suspected lesions. Imaging includes CT or MRI scans of the chest, abdomen, or pelvis. Brain CT or MRI is performed for subjects with known or suspected brain metastasis, while bone scan and/or bone X-ray scan is performed for subjects with known or suspected bone metastasis.

Imaging assessment at screening must be performed within 28 days prior to the first study dose, and first tumor assessment during the treatment period should be performed 6 weeks (± 7 days) after starting study treatment. Imaging evaluation should be performed once every 2 cycles (6 weeks ± 7 days) in the first 12 months (first 16 cycles) during the treatment. Then it is performed once every 3 cycles (9 weeks ± 7 days) after 12 months until PD, lost to follow-up, death, withdrawal of informed consent, start of other anti-tumor treatment or study termination by the sponsor.

If the subject achieves CR or PR, conformation should be done at least 4 weeks (28 days) after the first evaluation. In case of SD, tumor assessment should be performed at least once after at least 6 weeks (± 7 days) after enrollment, and the measurements must meet the criteria for SD at least once.

The same imaging technique should be used in subsequent tumor evaluations for the same type of lesions as at screening. Anti-tumor activity assessment shall be carried out during the screening period and treatment process through radiography according to the study procedure; tumor evaluation should also be performed when progressive disease is suspected (such as exacerbation of symptoms) and upon withdrawal (if evaluation is not performed within the past 4 weeks).

All subjects should continue to undergo tumor assessments according to the study protocol, regardless of dose interruptions or dose delays. If discontinuation is indicated due to deterioration of overall health in absence of objective evidence of progressive disease, such event shall be reported as symptomatic deterioration. Objective progressive disease (i.e. confirmed radiographically) should be documented even after treatment discontinuation.

Evaluation is done according to RECIST 1.1.

Documentation and imaging data of all subjects must be accessible for source validation and peer review.

7.2 Safety Evaluation

7.2.1 Safety endpoints

Safety parameters for this study include clinical symptoms, vital signs, physical examination, laboratory tests (hematology, urinalysis, blood biochemistry, thyroid function, and coagulation function). AEs are evaluated according to NCI CTCAE Version 4.03, including type, incidence, severity, start and end date, whether it is an SAE, causality with the study drugs, and outcome.

7.2.2 Definition of adverse event

An adverse event (AE) refers to any untoward medical occurrence in a study subject administered a medicinal product and which does not necessarily have a causal relationship with this treatment. In this study, AEs should be documented from signing informed consent until the end of the safety follow-up period (90 days after the last dose of the study drugs) or the start of new anti-tumor treatment. AEs include any adverse symptoms or signs, abnormal laboratory tests or diseases. AEs include the following:

- 1) Worsening of pre-existing (prior to enrollment) medical conditions/diseases (including symptoms, signs, and laboratory test abnormalities);
- 2) Any new adverse medical conditions (including symptoms, signs, and newly diagnosed diseases);
- 3) Clinically significant abnormal laboratory findings.

The investigator should record any AEs that have occurred in detail, including the description of the AEs and all relevant symptoms, time of occurrence, severity, relationship to the investigational drugs, duration, measures taken, and final results and outcomes.

